4.7 Demographics, Baseline Characteristics, and Medical History

The demographics (age, gender, race, ethnicity, height, weight, and body mass index), and baseline characteristics from study RECAST SLE will be summarized. Table 2 provides the list of baseline characteristics to be summarized using the OLE safety analysis set.

Table 2Baseline Characteristics

Significant medical history finding from the RECAST SLE study will be summarized by MedDRA system organ class (SOC) and preferred term (PT) for the OLE safety analysis set.

4.8 Exploratory Efficacy Analyses

4.9 Safety Analyses

4.9.1 Adverse Events

Adverse events (AEs) collected in this OLE study will be summarized separately using the OLE safety analysis set and together with the AEs collected in study RECAST SLE using the any daxdilimab analysis set overall and by treatment group. Table 4 presents the definition of treatment-emergent adverse event (TEAE) for reporting purposes.

Study	Definition
OLE	A TEAE is defined as any AE with an onset date on or after the first dose date in the OLE study.

Study	Definition
OLE + RECAST SLE (Any daxdilimab exposure)	A TEAE is defined as any AE with an onset date on or after the first daxdilimab dose date (either in OLE or RECAST SLE study)

Table 4Definition of TEAEs

AEs will be coded using the most recent version of MedDRA. All TEAEs will be summarized overall and by MedDRA system organ class (SOC) and preferred term (PT), by severity and by relationship to daxdilimab. Specific AEs will be counted once for each participant for calculating rates, but all events will be presented in participant listings. In addition, if the same AE occurs multiple times within a particular participant, the highest severity and level of causality will be reported.

In addition, since the duration of exposure to daxdilimab is shorter for the participants who received placebo in the RECAST SLE study, the PYE adjusted incidence rate for the number of participants who experienced TEAE will be included in the combined summary of OLE + RECAST SLE using any daxdilimab analysis set. Refer to Section 4.6 for definition of PYE.

An overall summary table will be showing the number and percentage of participants with at least one event in any of the following categories:

- TEAE
- Treatment-emergent serious adverse event (TESAE)
- TEAE resulting in death
- Grade 3 or higher TEAE using CTCAE v5.0
- TEAE leading to discontinuation of daxdilimab
- Serious and/or grade 3 or higher TEAE
- Daxdilimab related TEAE
- Daxdilimab related TESAE

The following AE summaries will also be provided by SOC and PT:

- TEAEs
- TEAEs resulting in death
- Grade 3 or higher TEAEs using CTCAE v5.0
- TEAE leading to discontinuation of daxdilimab
- Daxdilimab related TEAE
- TESAEs
- Daxdilimab related TESAE

An AE of special interest (AESI) is an AE of scientific and medical interest specific to understanding of the IP and may require close monitoring and collection of additional information by the Investigator. AESIs for this protocol include:

- Hypersensitivity reaction, including anaphylaxis
- Severe (Grade 3 or higher) viral infections/reactivations

- Opportunistic infection as listed in the Appendix 6 of the protocol (all cases)
- Malignancy (except non-melanoma skin cancer)

Treatment emergent AESIs will be summarized by SOC and PT. TESAEs will be summarized by serious adverse event (SAE) criteria as well. A summary of TEAEs sorted by frequency will be presented by PT.

Listings will be provided for all TEAEs and non-treatment emergent AEs collected in this OLE study and RECAST SLE.

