1.3 Schedule of Activities

The tests and assessments to be conducted during the study and the timing for such tests/assessments are provided in Table 1.

Table 1 Schedule of Activities

Study Day	Treatment									Follow-Up	
	1	29/57	85	113/141	169	197/225	253	281/309	337	365	393
Week (window)	0	4/8 (± 3 d)	12 (± 7 d)	16/20 (± 3 d)	24 (± 7 d)	28/32 (± 3 d)	36 (± 7 d)	40/44 (± 3 d)	48/ET (± 7 d)	52 (± 7 d)	56 (± 7 d)
Procedure/Visit Number	V1 ^a	V2/V3 ^b	V4	V5/V6 ^b	V7	V8/V9 ^b	V10	V11/V12 ^b	V13	V14	V15
General Assessments/Procedures											
ICF	X										
Eligibility review	X										
Review medical history and add any AEs/SAEs/AESIs from RECAST SLE (if appropriate)	X										
12-lead ECG (after 10 minutes rest in supine position) ^c	X				X				X		X
Vital signs and weight ^d	X		X		X		X		X	X	X
Physical examination ^e	X		X		X		X		X	X	X
Laboratory Assessments											
Urine pregnancy test (in women of childbearing potential)	X		X		X		X		X	X	X
FSH ^g	X										
Hepatitis B DNA testing ^h	X		X		X		X		X		X
Routine hematology and chemistry	X		X		X		X		X	X	X
HbA1c	X				X				X		X

Table 1 Schedule of Activities

Study Day	Treatment									Follow-Up	
	1	29/57	85	113/141	169	197/225	253	281/309	337	365	393
Week (window)	0	4/8 (± 3 d)	12 (± 7 d)	16/20 (± 3 d)	24 (± 7 d)	28/32 (± 3 d)	36 (± 7 d)	40/44 (± 3 d)	48/ET (± 7 d)	52 (± 7 d)	56 (± 7 d)
Procedure/Visit Number	V1 ^a	V2/V3 ^b	V4	V5/V6 ^b	V7	V8/V9 ^b	V10	V11/V12 ^b	V13	V14	V15
Lipids (after an 8-hour fast; water allowed) ⁱ	X				X				X		
Urinalysis and spot UPCr ^j	X		X		X		X		X	X	X
Confirmatory tests for hemolytic anemia ^k	X		X		X		X		X	X	X
C3 and C4	X		X		X		X		X	X	X
Anti-dsDNA antibodies	X		X		X		X		X	X	X
Anti-Smith antibodies	X								X		
ANA, anti-RNP, anti-SSA, anti-SSB, rheumatoid factor	X ^l								X		
PT/INR and PTT	X		X		X		X		X		X
Serum IgG, IgA, IgM	X		X		X		X		X		X
Serum IFN α	X		X		X		X		X		X
hs-CRP	X		X		X		X		X	X	X
pDC FACS	X		X		X		X		X		X
Blood MxA	X				X				X		X
Daxdilimab PK (serum)	X		X		X		X		X		X
Daxdilimab ADA	X		X		X		X		X		X

Table 1 Schedule of Activities

Study Day	Treatment									Follow-Up	
	1	29/57	85	113/141	169	197/225	253	281/309	337	365	393
Week (window)	0	4/8 (\pm 3 d)	12 (\pm 7 d)	16/20 (\pm 3 d)	24 (\pm 7 d)	28/32 (\pm 3 d)	36 (\pm 7 d)	40/44 (\pm 3 d)	48/ET (\pm 7 d)	52 (\pm 7 d)	56 (\pm 7 d)
Procedure/Visit Number	V1 ^a	V2/V3 ^b	V4	V5/V6 ^b	V7	V8/V9 ^b	V10	V11/V12 ^b	V13	V14	V15
Questionnaires ^m											
PtGA	X		X		X		X		X		X
PGIC	X		X		X		X		X		X

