8.4.1 Definitions

- **Adverse event:** An AE is any untoward medical occurrence in a subject administered a pharmaceutical product and that does not necessarily have a causal relationship with this treatment. An AE can therefore be any unfavorable and unintended sign (including an abnormal laboratory finding), symptom, or disease (new or exacerbated) temporally associated with the use of an IP, whether or not considered related to the IP. Events that meet and do **not** meet the AE definition are provided in Appendix 2, [Section 10.2.1](#).
- **Serious adverse event:** An event is considered “serious” if, in the view of either the Investigator or Sponsor, it results in any of the following outcomes:
 - Death
 - A life-threatening AE (An event is considered “life-threatening” if, in the view of either the Investigator or Sponsor, its occurrence places the subject(s) at immediate risk of death. It does not include an AE or suspected adverse reaction that, had it occurred in a more severe form, might have caused death.)
 - Inpatient hospitalization or prolongation of existing hospitalization
 - A persistent or significant incapacity or substantial disruption of the ability to conduct normal life functions
 - A congenital anomaly/birth defect

- Important medical events that may not result in death, be life-threatening, or require hospitalization may be considered serious when, based upon appropriate medical judgment, they may jeopardize the subject(s) or may require medical or surgical intervention to prevent one of the outcomes listed in this definition.

Additional information is provided in Appendix 2, [Section 10.2.2](#).

- **Adverse reaction:** An adverse reaction is any AE caused by a drug.
- **Adverse event of special interest:** An AESI is an AE of scientific and medical interest specific to understanding of the IP and may require close monitoring and collection of additional information by the Investigator. An AESI may be serious or nonserious. The rapid reporting of AESIs allows ongoing surveillance of these events in order to characterize and understand them in association with the use of this IP.

The following AESIs will be particularly monitored in this study:

- Hypersensitivity reaction, including anaphylaxis
- Severe (Grade 3 or higher) viral infections/reactivations
- Opportunistic infection as listed in Appendix 6, [Section 10.6](#) (all cases)
- Malignancy (except nonmelanoma skin cancer)

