9.3.2 Primary Endpoint(s) Analysis

9.3.2.1 Safety Analysis

Adverse events will be coded using the Medical Dictionary for Regulatory Activities by system organ class (SOC) and preferred term (PT). In general, if an AE onset is on or after the first OLE dose date, the AE will be considered as a treatment-emergent AE (TEAE) for OLE. All TEAEs will be summarized overall and by SOC and PT, as well as by severity and by relationship to daxdilimab.

For the summary of TEAEs by severity, each participant will be counted only once within a SOC or a PT by using the AEs with the highest intensity within each category. For the summary of TEAEs by relationship to IP, each participant will be counted only once within a SOC or a PT by using the AEs with the greatest reported relationship within each category. TEAE leading to discontinuation of daxdilimab will be summarized by SOC and PT. Treatment-emergent SAEs and treatment-emergent AESIs will also be summarized.

Clinically significant abnormalities in laboratory parameters, vital signs, ECGs, and physical examinations will be recorded as AEs or SAEs. Laboratory assessments, vital signs, and ECGs, as well as their changes from baseline at each visit will also be summarized descriptively.

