10.2.1 Definition of AE

AE Definition

- An AE is any untoward medical occurrence in a subject administered a pharmaceutical product and that does not necessarily have a causal relationship with this treatment. An AE can therefore be any unfavorable and unintended sign (including an abnormal laboratory finding), symptom, or disease (new or exacerbated) temporally associated with the use of an IP, whether or not considered related to the IP.

Events Meeting the AE Definition

- Any abnormal laboratory test results (hematology, clinical chemistry, or urinalysis) or other safety assessments (eg, ECG, radiological scans, vital signs measurements), including those that worsen from baseline, considered clinically significant in the medical and scientific judgment of the Investigator (ie, not related to progression of underlying disease, or more severe than expected for the subject's condition)
- Exacerbation of a chronic or intermittent pre-existing condition including either an increase in frequency and/or intensity of the condition
- New condition detected or diagnosed after IP administration even though it may have been present before the start of the study
- Signs, symptoms, or the clinical sequelae of a suspected drug-drug interaction
- Signs, symptoms, or the clinical sequelae of a suspected overdose of either IP or a concomitant medication. Overdose per se will not be reported as an AE/SAE unless it is an intentional overdose taken with possible suicidal/self-harming intent. Such overdoses should be reported regardless of sequelae.

Events not Meeting the AE Definition

- Any abnormal laboratory findings or other abnormal safety assessments that are associated with the underlying disease, unless judged by the Investigator to be more severe than expected for the subject's condition
- The disease/disorder being studied or expected progression, signs, or symptoms of the disease/disorder being studied, unless more severe than expected for the subject's condition
- Medical or surgical procedure (eg, endoscopy, appendectomy): the condition that leads to the procedure is the AE
- Situations in which an untoward medical occurrence did not occur (social and/or convenience admission to a hospital)
- Anticipated day-to-day fluctuations of preexisting disease(s) or condition(s) present or detected at the start of the study that do not worsen

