2 TRIAL OVERVIEW

2.1 Trial Objectives and Endpoints

The objectives and corresponding endpoints are listed in Table 1 below:

Table 1 Primary, Secondary, and Exploratory Objectives

Objectives	Endpoints		
Primary Objective			
To evaluate the long-term safety and tolerability of 200 mg Q12W daxdilimab	Incidence of AEs, SAEs, and AESIs		
Secondary Objectives			
To characterize the PK, PD, and immunogenicity of daxdilimab	Daxdilimab concentrations, change in pDCs, and ADA rate		
Exploratory Objectives			
ADA = anti-drug antibodies; AE =	= adverse event; AESI = AE of special interest; PD =		
pharmacodynamic(s); pDC = plasmacytoid dendritic cell; PGA = Physician Global Assessment; PK,			
pharmacokinetic(s); Q12W = every 12 weeks; RECAST SLE = Phase 2 Randomized, Double-Blind, Placebo- Controlled Efficacy and Safety Study of daxdilimab for the Treatment of Moderate to Severely Active			

Systemic Lupus Erythematosus;

SAE = serious AE; SLE = systemic

lupus erythematosus; SLEDAI-2K = Systemic Lupus Erythematosus Disease Activity Index 2000.

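### TEAEs are defined by onset date alone and no rule covers grade increases in AEs ongoing from RECAST, so worsening after the first OLE dose may be omitted or counted inconsistently

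*SAP*

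**What the plan says.** The primary endpoint is "Incidence of AEs, SAEs, and AESIs" (SAP 2.1). It is tabulated through treatment-emergent summaries.

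- **SAP 4.9.1, Table 4, OLE row:** "A TEAE is defined as any AE with an onset date on or after the first dose date in the OLE study".
- **SAP 4.9.1, Table 4, pooled row:** "any AE with an onset date on or after the first daxdilimab dose date (either in OLE or RECAST SLE study").
- **Protocol 9.3.2.1:** "In general, if an AE onset is on or after the first OLE dose date, the AE will be considered as a treatment-emergent AE". The opening qualifier suggests exceptions, but none is defined.

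No worsening clause appears in any of these places or elsewhere in the two documents. AEs that are not treatment-emergent are listed only (SAP 4.9.1).

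The AE definition is wider. Protocol 8.4.1 covers a "symptom, or disease (new or exacerbated) temporally associated with the use of an IP", and Appendix 2 (10.2.1) lists as an AE "Exacerbation of a chronic or intermittent pre-existing condition including either an increase in frequency and/or intensity of the condition".

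At Visit 1 the Schedule of Activities (protocol 1.3) has sites "Review medical history and add any AEs/SAEs/AESIs from RECAST SLE (if appropriate"). Protocol 8.4.2 asks for onset, resolution and severity for each AE, but gives no instruction for a change of grade. Appendix 2 (10.2.3), under follow-up, directs that updates be entered in the documents first submitted.

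**The concern.** In a roll-over study some AEs can be expected to be ongoing at the first OLE dose, because OLE Day 1 is meant to coincide with RECAST Week 48. If one of them rises in grade or becomes serious after that dose, its place in the tables depends on how the site records it. A new record has an OLE onset date and is a TEAE. An update to the old record keeps the RECAST onset date and fails the Table 4 test.

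Safety incidence is the sole primary purpose of the study. The rows exposed are all TEAEs, Grade 3 or higher, treatment-emergent SAEs, AESIs, and TEAEs leading to discontinuation. Any omission can only lower these counts. The former placebo group matters most, because for them worsening after OLE Day 1 is worsening after first exposure to daxdilimab.

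**Working it through.** **1. Planned size.** Inputs are 195 randomized in RECAST and 20% premature discontinuation (protocol 9.5, SAP 2.3). 195 x (1 - 0.20) = 156, which reproduces the stated figure. No hypothesis is tested, so no power calculation applies.

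**2. Where the event goes.** Take an AE that is ongoing at the first OLE dose and worsens afterwards.

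| RECAST arm and onset | How the site records it | OLE summary | Pooled summary |
|---|---|---|---|
| Daxdilimab, began after first RECAST daxdilimab dose | Old record updated | Not a TEAE | TEAE |
| Daxdilimab, began after first RECAST daxdilimab dose | New record | TEAE | TEAE |
| Placebo, began on placebo | Old record updated | Not a TEAE | Not a TEAE |
| Placebo, began on placebo | New record | TEAE | TEAE |

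For a former placebo participant the first daxdilimab dose is the first OLE dose, so both Table 4 rows apply the same cut-off date.

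**3. Do other outputs recover it?**

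- The highest-severity rule (protocol 9.3.2.1, SAP 4.9.1) works within the TEAE summaries. It does not bring in an event with an earlier onset.
- Laboratory toxicity grades (SAP 4.9.2) are tabulated whatever the AE onset, but cover laboratory values only. The shifts use a baseline before the first RECAST dose (SAP 4.1.1), so they do not isolate change after OLE Day 1.
- Disposition (SAP 4.5) gives reasons for discontinuation. An AE that worsened and led to discontinuation could appear there and yet be absent from the table of TEAEs leading to discontinuation.
- One AESI is defined by grade: viral infection or reactivation of Grade 3 or higher. A lower-grade infection ongoing at Day 1 could become an AESI by worsening and still fail the onset test.

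**4. Size.** The documents give no rate of carried-over AEs or of worsening. At the planned size, one omitted participant moves an OLE row by 1/156 = 0.64 percentage points.

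An illustration of a single row, on assumed rates: if 20% to 40% of participants enter with an ongoing AE, 10% of those worsen, and no site opens a new record, then 156 x 0.20 x 0.10 = 3.1 and 156 x 0.40 x 0.10 = 6.2 participants, or 2% to 4%.

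For overall TEAE incidence, a missed worsening matters only if the participant has no other TEAE. Using the 73% with an AE on daxdilimab in Phase 1b (protocol 2.2.5.2) as a stand-in, and assuming independence:

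- 3.1 x (1 - 0.73) = 0.8 participants, 0.8/156 = 0.5%
- 6.2 x (1 - 0.73) = 1.7 participants, 1.7/156 = 1.1%

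A second illustration starts from 0.73 x 156 = 114 participants with a TEAE by onset and 42 without. If 0%, 5%, 10% or 20% of the 42 had an unrecorded worsening, the clause would add 0, 2, 4 or 8 participants. Incidence would go from 73.1% to 73.1%, 74.4%, 75.6% or 78.2%.

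**The case against.** The strongest reply is that the plan already captures these events. RECAST AEs join the medical-history review at Visit 1, which makes them pre-existing conditions at OLE entry. Appendix 2 makes exacerbation of such a condition an AE in its own right. Worsening after Day 1 would then have an OLE onset, and Table 4 as written would count it. The eCRF completion guidelines, which are not among these documents, may also contain the recording rule.

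This stands in part. A reader might infer from Table 4 that every carried-over AE that worsens is excluded from the primary endpoint. The documents do not support that, since a worsening logged as a new AE is counted. But neither document requires a new record, and the follow-up text in 10.2.3 can fairly be read as updating the old one. Sites could follow either reading.

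Two further points stand. Protocol 5.2 excludes unresolved herpes zoster, cytomegalovirus or Epstein-Barr infection and clinically significant active infection at Visit 1, and 5.1 excludes those who stopped IP early in RECAST. This limits carry-over of infection AESIs and of AEs that led to stopping. Also, a worsening clause in Table 4 can be programmed only if grade changes are dated, so the recording rule does most of the work.

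**Conclusion.** The gap is real but conditional. Both Table 4 rows and protocol 9.3.2.1 rest on onset date alone, and no recording rule settles what happens to an ongoing RECAST AE that worsens or becomes serious. Such events may be omitted or counted inconsistently across sites, and any error is downward. The pooled summary is exposed essentially for former placebo participants only.

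The size is unknown. The 3 to 6 participants in a row, and the 0 to 8 added to overall incidence, rest on assumed rates, and the former also assumes that no site opens a new record. A reader might also infer that the loss falls mostly in the higher-grade rows. That cannot be shown, since a Grade 1 to Grade 2 worsening never reaches the Grade 3 or higher table. Nor do the events vanish from the report, because they remain in the listings.

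The sample size is unaffected. Non-serious worsening of SLE, which protocol 8.4.2 exempts from AE reporting, is a separate matter.

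**What to change.** 1. In protocol 8.4.2 and the eCRF completion guidelines, instruct sites to record a grade increase, or a change to serious, in an AE ongoing at the first OLE dose as a new AE with its own onset date. State that this takes precedence over updating the original record.
2. In both rows of SAP Table 4 and in protocol 9.3.2.1, add: *or that started before and worsened in severity or became serious on or after that dose*. This brings the TEAE definition into line with the AE definition and covers any record that was updated with a dated change.

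The cost is one extra recording rule for sites and one clause in each definition. Reported TEAE incidence may rise slightly. A new record for an event already counted in the pooled summary does not double-count the participant, because each participant is counted once per term.

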2.3 Sample Size Determination

Sample size determination is based on the number of participants who have completed the treatment period of Study VIB7734.P2.S1 (RECAST SLE). A total of 195 participants have been randomized in the RECAST SLE study. Assuming that 20% of participants will prematurely discontinue treatment, there will be a total of approximately 156 participants who will be eligible for this long-term safety study.

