4.1.3 Missing Data

In general, missing data will not be imputed unless methods for handling missing data are specified.

4.2 **Protocol Deviations**

The protocol deviations are reviewed and categorized as major and minor prior to the database lock. The number and percentage of participants with major protocol deviations by deviation reason (eg, nonadherence to study drug, violation of select inclusion/exclusion criteria) will be summarized. A by-participant listing will be provided for all protocol deviations.

A by-participant listing will be provided for those participants who did not meet at least one eligibility (inclusion or exclusion) criterion. The listing will present the eligibility criterion (or criteria if more than one deviation) that participants did not meet and related comments, if collected.

4.3 **Primary Hypothesis**

No formal statistical hypothesis will be evaluated.

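### SAP 4.9.1 names the person-year adjusted rate only for TEAEs in the combined OLE + RECAST SLE summary and leaves open whether serious events and AESIs get it too

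*SAP*

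**What the plan says.** The primary endpoint is "Incidence of AEs, SAEs, and AESIs" (SAP 2.1). SAP 4.9.1 plans two sets of adverse event summaries. One covers the OLE alone, in the OLE safety analysis set. The other combines OLE and RECAST SLE events, "using the any daxdilimab analysis set overall and by treatment group".

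For the combined summary the SAP adds an exposure-adjusted rate and gives its reason: "since the duration of exposure to daxdilimab is shorter for the participants who received placebo in the RECAST SLE study". The commitment is that "the PYE adjusted incidence rate for the number of participants who experienced TEAE will be included in the combined summary".

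The overall table that follows lists TEAEs, TESAEs, deaths, Grade 3 or higher events and discontinuations as separate rows, and the measure stated for it is number and percentage. AESIs are not a row of that table. On them the SAP says "Treatment emergent AESIs will be summarized by SOC and PT" and states no measure, so the SAP 4.1 default for categorical variables (number and percentage) applies.

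SAP 4.6 defines any-daxdilimab exposure from the first daxdilimab dose in either study to the last dose date in the OLE, plus 28 days. SAP 4.4.3 defines the any daxdilimab set as everyone with at least one daxdilimab dose in either study.

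**The concern.** The SAP's reason for adjusting is unequal exposure between the groups. That reason applies to SAEs and AESIs as much as to TEAEs, and crude percentages of rare events track exposure almost in proportion. Most participants have some TEAE in any case, so the any-TEAE percentage saturates and is distorted less. The rate is therefore named where the distortion of the crude figure is smallest and left unstated where it is largest.

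If the tables are programmed to the letter, participants on daxdilimab in both studies would show a higher percentage of SAEs, opportunistic infections or malignancies than former placebo participants even when the underlying rate is the same. That could be misread as an effect of cumulative exposure, or a real difference could be obscured.

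**Working it through.** **The plan's own figure.** SAP 2.3 gives 195 randomized in RECAST SLE and 20% premature discontinuation: 195 × (1 − 0.20) = 156, as stated. The 20% is used again below.

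**Inputs.** OLE doses are at Weeks 0, 12, 24, 36 and 48, so first to last dose is 336 days (Protocol 6.1). The RECAST treatment period runs through Day 337, also 336 days (Protocol 5.1). OLE Day 1 coincides with RECAST Week 48 (Protocol 5.5). Exposure is last dose date + 28 − first dose date + 1, and PYE is days / 365.25 (SAP 4.6). Assumed: first RECAST daxdilimab dose on Day 1, and no gap between the studies. The documents give neither the RECAST dosing schedule nor its allocation.

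**Completers.**
- Former placebo: 336 + 28 + 1 = 365 days = 1.00 PY.
- Daxdilimab in both studies: 336 + 336 + 28 + 1 = 701 days = 1.92 PY.
- Ratio: 701 / 365 = 1.92. Counting event collection through Week 56 instead gives (336 + 393) / 393 = 729 / 393 = 1.85.

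**Group level.** The any daxdilimab set also holds RECAST daxdilimab participants who never entered the OLE. Take 20% of that group as not continuing, with a fraction m of the RECAST period (assumed 0.25 to 1.00) and the same 28-day tail, so 336m + 29 days each.
- No OLE discontinuation: mean exposure is 0.80 × 701 + 0.20 × (336m + 29), which is 583 days (m = 0.25) to 634 days (m = 1.00). Against 365 days the ratio is 1.60 to 1.74.
- 20% OLE discontinuation at mid-period (assumed): former placebo 0.80 × 365 + 0.20 × 197 = 331 days. OLE entrants already on daxdilimab 0.80 × 701 + 0.20 × 533 = 667 days, so their group has 557 to 607 days. The ratio is 1.68 to 1.83.
- With 30% not continuing instead of 20%, the ratio is 1.44 to 1.74 across the same assumptions.

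**Effect on percentages.** Assume the same constant rate in both groups. The crude percentage is 1 − exp(−rate × PYE), and the adjusted rate is participants with an event / total PYE. For completers (former placebo vs daxdilimab in both studies):

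| Assumed true rate per 100 PY | Crude % | Crude ratio | PYE-adjusted rate per 100 PY |
|---|---|---|---|
| 2 | 2.0 vs 3.8 | 1.90 | 2.0 vs 2.0 |
| 5 | 4.9 vs 9.2 | 1.88 | 4.9 vs 4.8 |
| 10 | 9.5 vs 17.5 | 1.84 | 9.5 vs 9.1 |
| 150 | 77.7 vs 94.4 | 1.22 | 77.7 vs 49.2 |

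At group level, with a rate of 5 per 100 PY, 20% not continuing and no OLE discontinuation:
- m = 0.25: 0.80 × 9.15% + 0.20 × 1.53% = 7.63% against 4.87%, a ratio of 1.57.
- m = 1.00: 0.80 × 9.15% + 0.20 × 4.87% = 8.29% against 4.87%, a ratio of 1.70.

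With the assumed OLE discontinuation the ratios are 1.65 (7.29% vs 4.43%) to 1.80 (7.96% vs 4.43%). For rates up to about 5 per 100 PY, the spurious crude ratio is therefore roughly 1.6 at group level to 1.9 in completers. At 10 per 100 PY the lowest group-level value is 1.53 (14.58% vs 9.51%).

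Dividing by total PYE nearly removes the artefact for rare events. For very common events it over-corrects (last row), because exposure is not stopped at the first event. The rate thus works best for the rows where the SAP does not name it.

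**The case against.** The strongest reply is that TESAEs and AESIs are subsets of TEAEs under SAP Table 4, and that the death, Grade 3 and discontinuation rows are worded as TEAEs. The sentence on the rate precedes all the table lists, and table layout is deferred to the Statistical Programming Plan. The number-and-percentage sentence cannot prove exclusion either, because the TEAE row itself carries both measures. This stands. A reader might infer that the SAP excludes SAEs and AESIs from adjustment, but no sentence says so. The defect is unspecified scope, which two programmers could resolve differently.

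A reader might also infer that the primary analysis is distorted, since SAEs and AESIs belong to the primary endpoint. The documents do not support that. Protocol 9.3.2.1 counts events from the first OLE dose, and the SAP reports them separately in the OLE safety analysis set, where every participant has the same planned exposure.

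A third tempting inference is that percentages would simply double. The 1.92 ratio belongs to participants who complete both studies, whereas the analysis set also includes those who stopped in RECAST.

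Finally, the study is descriptive ("No formal statistical hypothesis will be evaluated"), and SAP 4.6 plans to tabulate exposure and total person-years across both studies, so an alert reader could see the imbalance. That lowers the risk of misreading. It does not put the right measure beside the SAE and AESI counts.

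**Conclusion.** The point holds as a gap in the supportive combined summary. SAP 4.9.1 gives a reason for exposure adjustment that covers SAEs and AESIs but names the rate only for TEAEs. Read literally, the plan shows TESAEs and AESIs by group unadjusted. With equal true rates of rare events, that would produce crude ratios of roughly 1.6 to 1.9.

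The upper end rests on full completion of both studies. The lower end rests on the documents' 20% discontinuation and on assumed partial exposure in those who did not continue. Both assume a constant event rate, and the rates themselves are illustrative because the documents give none. The OLE-only primary summary is unaffected. This is a cheap improvement in clarity, not an error that threatens the trial's main result.

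**What to change.** Two edits, made together.

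1. SAP 4.9.1: state that in the combined OLE + RECAST SLE summary the PYE-adjusted incidence rate is reported, overall and by treatment group, for TEAEs, TESAEs and treatment-emergent AESIs (overall and per AESI category), and for the Grade 3 or higher, death and discontinuation rows.
2. SAP 4.6: define any-daxdilimab exposure by the last daxdilimab dose in either study. The current formula needs a last OLE dose date, so PYE cannot be computed for RECAST daxdilimab participants who never entered the OLE, although SAP 4.4.3 includes them. Without this edit, the first would extend a rate whose denominator is undefined for part of the set.

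The cost is extra columns in tables already planned and a small amount of programming. No new data are needed, and the OLE-only summaries do not change.
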